#### *5.4 Stereotactic Body Radiotherapy Risks*

Short-term side effects include but not limited to skin reaction, local hair loss, fatigue, abdominal pain, nausea, vomiting, diarrhea, increasing liver function abnormality, GI bleeding or perforation which may require surgical intervention. Long term side effects are less likely to occur but if they do occur are more likely to be permanent. They include local hair loss, liver function abnormality, diarrhea, small bowel obstruction which may require surgical intervention, spinal cord injury which could result in paralysis, and kidney function abnormality.

#### *5.3.4 Fiducial placement*

It is currently standard practice at our institution for the operating surgeon to place fiducial markers intraoperatively at the areas he feels will be at risk for positive or close margins. As such, patients will not need to undergo a separate procedure for fiducial marker placement.

#### 5.3.5 *CT Risks*

The subject will be exposed to radiation associated with the CT scans performed to assess response to therapy. CT scans are routinely performed as standard-of-care for tumor staging and to monitor response to therapy, and the radiation dose associated with these diagnostic scans are felt to represent minimal risk.

Claustrophobia: Possible anxiety, claustrophobia, and/or temporary discomfort may occur as a result of being placed in the scanning devices. Subjects will be monitored and removed from the scanner if required

## 6.0 STUDY EVALUATIONS

### 6.1 Pretreatment evaluation

The following tests/procedures will be performed in order to ascertain subject eligibility within 28 days prior to registration unless otherwise specified.

- 6.1.1 Medical history
- 6.1.2 Physical examination, including Karnofsky status, ECOG performance status and vital signs.
- 6.1.3 Signed informed consent
- 6.1.4 Subject body weight and height taken within 1 week of the study start.
- 6.1.5 Histologic and/morphologic confirmation of diagnosis as well as margin status
- 6.1.6 CBC including: WBC with complete differential, platelets, RBC, hemoglobin, hematocrit, within 30 days prior to study start.
- 6.1.7 Blood chemistries including BUN, creatinine, total bilirubin, AST, ALT, alkaline phosphatase, sodium, potassium, calcium, phosphorus, chloride, magnesium within 30 days of study start.
- 6.1.8 Urine or blood HCG test for female subjects of child-bearing potential (women who are not at least 1 year post-menopause or who have not undergone a surgical sterilization procedure) within 14 days prior to study start. Female subjects of child-bearing potential will be instructed to use contraception from the time of the screening pregnancy test until study completion.
- 6.1.9 CT of the abdomen and pelvis

### 6.2 Evaluation during treatment

The subjects will be carefully followed while on active treatment and post-treatment for 24 months, or until death. Evaluation during treatment will consist of the following activities:

- 6.2.1 Administration of SBRT
- 6.2.3 Interim medical history and physical examination at baseline, prior to SBRT treatment, at the end of SBRT, and 10-12 weeks after SBRT then every 3 months thereafter for up to 24 months.
- 6.2.4 Serum chemistry and electrolytes to include BUN, creatinine, sodium, potassium, bicarbonate, chloride, calcium, magnesium, glucose, total bilirubin, AST, ALT, alkaline phosphatase post-treatment as clinically indicated
- 6.2.5 Hematologic studies to include CBC with differential and platelet count prior to SBRT and repeated 10-12 weeks later and then at follow-up as clinically indicated.
- 6.2.6 CT scan will be obtained at 10-12 weeks post-treatment and will be reviewed for evidence of response. Since these subjects will likely have no gross disease on imaging, the main goal of the follow-up scans is to monitor for local and distant progression as defined below.

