#### *5.3 On-Treatment assessment and post-treatment toxicity evaluation*

All subjects will be seen prior to delivery of each fraction of SBRT with toxicity evaluated by physical examination. Subsequently, subjects will be evaluated for toxicity 10-12 weeks later and then every 3 months until at least 2 years. Toxicities will be scored by the NCI CTC AE version 4.0. Also see Section 6.0.

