### 6.3 Treatment schedule

Parameter	Pre-Study	SBRT			10-12 weeks post-treatment	Q 3 months until 24 months
		Fx 1	Fx 2	Fx3		
History	X	X		X	X	X
Physical exam	X	X		X	X	X
Measurement of disease	X				X	X
Performance Status	X				X	X
Serum Chemistry	X*				X ▲	X ▲
Hematologic Studies including CBC	X*				X	X ▲
CT Scan	X				X	X Ω
Serum or Urine Pregnancy Test for WOCBP	X					
Histologic and Morphologic Confirmation and Margin Status	X					
QOL assessment	X				X	X

\* Within 30 days of study start

▲If clinically indicated

ΩMay be modified by oncology team if patient receives system therapy

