### 6.4 Post-treatment evaluation and plan

#### 6.4.1 Evaluation of CT Imaging

A follow-up CT scan will be obtained at 10-12 weeks post-SBRT and then every 3 months until end of study. If the patient goes on to receive systemic therapy, the follow-up CT schedule can be modified at the discretion of the oncology team.

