### 7.2 Sample Size and Accrual Rate

#### 7.2.1 Sample Size

From the Investigators' treatment experience, the 2-year local progression-free survival rate for the standard of care is 40%. This phase II study aims to improve it to 60% with SBRT. We plan to have 24 months of accrual, and 24 months of follow-up beyond the last patient enrolled on study. Under assumption of exponential survival, a total of 50 patients will provide 94% power to detect a statistically significant improvement in survival by one-sided log-rank test at significance level 0.05. Assuming that there will be no loss to follow up and no ineligible case, a total of 50 patients will be accrued for this trial.

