#### 7.3.3 Analysis of Study Endpoints

Survival (LPFS, OS, TTP) will be estimated by the Kaplan-Meier method for all evaluable patients and the corresponding median survival times (with 95% confidence interval) reported. The 2-year LPFS will also be estimated along with its 95% confidence interval. The effect of variables listed in Section 7.3.2 will be explored with Cox regression models.

For the QOL data analysis, each item of the FACT-G will be individually assessed. The mean and standard deviation of the observed data will be summarized at each collection time and plotted against time, from baseline through the end of patient follow-up. Generalized linear models (such as cumulative logit models) for repeated measures will be used to explore if there are significant changes in HRQOL over time.

Using NCI Common Terminology Criteria for Adverse Events (CTCAE v4.0), the number of patients experiencing adverse events over their course of treatment will be characterized by type of adverse event and grade, by the time of onset in relation to the first day of therapy, and whether the event is clinically significant. Attribution of adverse events to treatment (unrelated, unlikely, possibly, probably, or definitely) will also be summarized for any serious adverse events (SAEs), CTCAE grade 3 or higher. The percentage of patients experiencing SAEs that are considered to be treatment-related (probable or definite) will be determined. The percentage of patients experiencing the acute and late toxicities associated with SBRT (as defined in Section 6.4) will also be estimated along with its 95% confidence interval.

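### Sections 6.2 and 6.3 end scheduled follow-up at 24 months per patient, against 24 to 48 months in 7.2.1; following the table would cut power from 94% to about 88% and usually leave the OS confidence interval open-ended

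*Combined protocol and SAP*

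**What the plan says.** The combined protocol and SAP gives several end points for follow-up of the same patient.

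- Section 6.2: "The subjects will be carefully followed while on active treatment and post-treatment for 24 months, or until death". Item 6.2.3 likewise limits history and physical examination to 24 months.
- Section 6.3, last column of the schedule: "Q 3 months until 24 months". No row covers vital status or survival contact.
- Section 5.3, for toxicity: "every 3 months until at least 2 years", so two years is a minimum.
- Section 6.4.1, for CT: "every 3 months until end of study", although the oncology team may modify the schedule if systemic therapy is given.
- Section 7.2.1: "We plan to have 24 months of accrual, and 24 months of follow-up beyond the last patient enrolled on study". The study therefore ends at month 48, and the first patients have up to 48 months of potential follow-up.

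Section 7.3.3 estimates LPFS, OS and TTP by Kaplan-Meier, with "the corresponding median survival times (with 95% confidence interval) reported", and adds the 2-year LPFS with its 95% interval. It plans no landmark estimate for OS. Section 6.4.2 counts only local progression as an LPFS event; death is not an event.

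**The concern.** The visit schedule is what a site works from. Taken literally, it gives every patient about 24 months of data, whereas the sample size section credits all but the last enrollees with more. Two things are at stake. The first is the primary comparison: power for a log-rank test depends on the number of events, and the events expected between months 24 and 48 would have no scheduled visit to find them. The second is the set of medians with intervals in 7.3.3. The design's own LPFS target implies a median beyond 24 months, and several OS medians quoted in the background lie close to 24 months. OS is a secondary objective, and no section schedules a survival contact after month 24, although the study stays open.

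**Working it through.** **Inputs.** From 7.2.1: N = 50; 2-year LPFS of 40% (null) and 60% (target); exponential times; 24 + 24 months; no loss to follow-up; "one-sided log-rank test at significance level 0.05"; and "a total of 50 patients will provide 94% power". From 1.2 and 1.3, OS medians in resected patients: 15.8, 19.7, 20, 21.2, 22 and 25.2 months. Assumed: uniform accrual, exponential OS, and the few days of treatment ignored, so that the cap is 24 months from enrollment.

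**Hazards.** Null: -ln(0.40)/24 = 0.0382 per month, median 18.2 months. Target: -ln(0.60)/24 = 0.0213 per month, median 24 × ln 2 / (-ln 0.60) = 32.6 months. Hazard ratio 0.557.

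**The plan's own figure.** One-sample log-rank, Z = (O - E)/√E, with analysis at month 48 and 40,000 simulated trials: power 94.3%. The stated 94% is reproduced.

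**Expected LPFS events at the target.**
- To month 48: 50 × [1 - (0.60 - 0.36)/(24 × 0.0213)] = 50 × (1 - 0.24/0.511) = 26.5.
- Capped at 24 months: 50 × (1 - 0.60) = 20.0.

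The same test under the cap has 88.1% power. If deaths censor LPFS, with an assumed OS median of 20 months, power is about 81% to month 48 and about 75% capped.

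**Medians under the cap.** With everyone followed to exactly 24 months and no earlier censoring, the Kaplan-Meier value at 24 months is a simple proportion.
- The median is reached if at least 25 of 50 patients have had the event.
- The log-log upper 95% limit is finite if the upper band at 24 months is at or below 0.5, that is, ln(-ln S) - 1.96 × √[(1 - S)/(50 S)]/(-ln S) ≥ ln(ln 2) = -0.367. With 32 events (S = 0.36) the left side is -0.340, which passes. With 31 (S = 0.38) it is -0.399, which fails. So 32 events are needed.

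Example, OS median 20 months: the probability of death by 24 months is 1 - 2^(-24/20) = 0.565, so the mean is 28.2 deaths with SD 3.51. P(at least 25) ≈ Φ((28.2 - 24.5)/3.51) = 0.85. P(at least 32) ≈ 1 - Φ((31.5 - 28.2)/3.51) = 0.17 to 0.18.

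Simulation with 3,000 to 4,000 trials per row agrees, and supplies the month-48 columns:

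| True value | Median reached, cap | Upper limit finite, cap | Median reached, month 48 | Upper limit finite, month 48 |
|---|---|---|---|---|
| OS 15.8 months | 99% | 62-64% | 100% | over 99% |
| OS 20 | 85-86% | 18% | 100% | 95% |
| OS 21.2 | 77-79% | 10-11% | over 99% | 91-92% |
| OS 22 | 72% | 8% | over 99% | 87-89% |
| OS 25.2 | 45-47% | 2% | 99% | 68-70% |
| LPFS 60% at 2 years | 9-10% | about 0% | 90% | 25-29% |
| LPFS 40% at 2 years | 94% | 32-34% | 100% | 98% |

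If deaths censor LPFS (assumed OS median 20 months), the LPFS median at the 60% rate is reached in about 13% of trials capped and 72-73% to month 48. Its upper limit is then finite in about 15% even at month 48.

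**The case against.** The best reply is that this is a conflict of wording, not a design that truncates survival. Sections 5.3, 6.4.1 and 7.2.1 all allow or require longer follow-up, 6.4.3 defines OS to death with no time limit, and 6.2 and 6.3 do not forbid later collection of vital status. That stands. A reader might infer that every assessment, survival included, stops at 24 months; the documents do not say so. They contradict one another, and the harm arises if sites follow the table.

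A reader might also infer that the OS median would usually be inestimable. It would not: at true medians of 15.8 to 22 months it is reached in 72-99% of trials under the cap. It falls below half only near 25 months, and the 25.2-month figure comes from a series restricted to R0 resections, unlike this population. What is usually lost, from about 20 months upward, is the upper confidence limit. A median with an upper limit not reached can still be reported.

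Third, longer follow-up does not rescue the LPFS interval. At the 60% target its upper limit stays open in roughly three trials in four, because 50 patients are few for a 32.6-month median. If LPFS is really 40%, the median is usually reached even with the cap.

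Finally, the primary objective is a rate with two years of follow-up, and its estimate at 24 months is unaffected. The loss of power in the log-rank comparison remains, and so does the lack of a planned OS landmark.

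**Conclusion.** The point holds as an internal contradiction with a measurable cost. If the 6.2/6.3 schedule governs, the primary test has about 88% power instead of 94%, with about 6.5 fewer expected events (26.5 - 20.0) at the target. The LPFS median at the target is then reached in about one trial in ten instead of nine in ten. For OS medians of 20 to 22 months, the upper limit is finite in 8-18% of trials instead of 87-95%.

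The power figures assume exponential times, uniform accrual, no dropout and no censoring of LPFS by death. With death censoring both powers are lower, and the gap is about 6 points (81% against 75%). The reproduction of 94% at month 48 supports the 24 + 24 reading but does not prove it: a cruder formula using the 30 events expected under the null at 24 months gives Φ(√30 × 0.584 - 1.645) = Φ(1.555) = 94.0% as well. The case rests on the explicit 24 + 24 statement in 7.2.1.

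The sponsor should correct this, but it does not undermine the 2-year LPFS estimate.

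**What to change.** Reconcile 5.3, 6.2, 6.2.3, the 6.3 table and 6.4.1 to a single end: the study end in 7.2.1, 24 months after the last patient is enrolled. After a patient's month 24, record at least vital status, date last known alive, and any local or distant progression found in routine care. Add a survival row to the 6.3 table. No extra scans need be made mandatory. The OS gain depends only on vital status. The full LPFS gain assumes that progression after month 24 continues to be looked for, as 6.4.1 already foresees.

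If the 24-month end is kept, restate the power in 7.2.1 for that follow-up (about 88% on the plan's own assumptions), and add 12- and 24-month OS with 95% confidence intervals to 7.3.3.

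The cost is a wording amendment and some added data entry, by record check or telephone contact, for surviving early enrollees while the study is open. No additional patients are needed.

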## 5.0 TREATMENT EVALUATION, ADMINISTRATION, AND MODIFICATION

### *SBRT guidelines*

#### *5.1 Tissue constraints*

Appropriate beam “nodes” or angles shall be selected to treat the primary site and areas at risk for occult disease spread. Careful target definition of these areas at risk is essential for optimal outcome. Beam shaping for treatment delivery shall be via conical or multi-leaf collimation (MLC). Treatment shall be via linear accelerator (LINAC) commissioned and equipped to deliver SBRT. Normal tissues and sensitive critical structures (e.g. duodenum, spinal cord, stomach, bowel, kidneys, liver, etc) shall be counteracted and the dose to these organs limited. See table below.

Normal Tissue Constraints	
Organ	Maximum Dose in 3 fractions
Liver (700 cm  )	15 Gy
1/3 of total kidney volume (left and right)	15 Gy
Spinal Cord	18 Gy
Stomach	30 Gy
Duodenum/small bowel	18 Gy

As discussed above the CTV will be equivalent to the PTV, unless the motion study reveals motion in the target volume. In that case, margins will be given to account for that motion.

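### Liver and kidney function abnormality are named SBRT risks, but no chemistry is required after SBRT, so their reported rates are lower bounds with an unknown shortfall

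*Combined protocol and SAP*

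**What the plan says.** **Named risks.** The short-term list in Section 5.4 includes "increasing liver function abnormality, GI bleeding or perforation which may require surgical intervention". The long-term list opens "They include local hair loss, liver function abnormality, diarrhea" and closes with "spinal cord injury which could result in paralysis, and kidney function abnormality". Liver is thus named for both periods and kidney for the later one only. The Section 5.1 constraint table has a row for each organ.

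**Baseline.** Section 6.1.7 requires "Blood chemistries including BUN, creatinine, total bilirubin, AST, ALT, alkaline phosphatase" and electrolytes for every subject.

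**After SBRT.** Section 6.2.4 lists creatinine, electrolytes and liver tests, ending "total bilirubin, AST, ALT, alkaline phosphatase post-treatment as clinically indicated". In the Section 6.3 table, the chemistry entries at 10-12 weeks and at the 3-monthly visits both carry the footnote "If clinically indicated". Text and table agree.

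**Blood counts.** Section 6.2.5 requires "CBC with differential and platelet count prior to SBRT and repeated 10-12 weeks later". Only the later counts are left to clinical indication.

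**Analysis.** Section 7.3.1 uses all evaluable patients for safety. Section 7.3.3 reports the percentage with acute and with late toxicity, each with a 95% confidence interval. Section 6.4.5 separates acute from late at 3 months after SBRT. Section 8.2.1 counts an abnormal laboratory finding as an adverse event. Section 3.5 leaves systemic therapy after SBRT to the medical oncologist.

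**The concern.** The plan names two organ-function risks that are graded from laboratory values and can be silent, then schedules no measurement of either after treatment. It does schedule a blood count, although Section 5.4 lists no haematological risk. A patient who is never tested enters the toxicity percentage as event-free.

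Acute and late toxicity is a secondary objective. At stake is whether a low or zero rate of liver or kidney abnormality can be read as evidence of safety, or only as evidence that few patients were tested. Testing will also follow co-treatment: a patient on chemotherapy is likely to have chemistry drawn, and a patient who declines it may not. The reported rate then depends partly on how many patients receive systemic therapy. The protocol does not require normal results or the number tested to be recorded, so the gap could not be corrected at analysis.

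**Working it through.** The plan states no expected liver or kidney toxicity rate, so there is no figure of its own to reproduce. Its one design calculation (94% power for local progression-free survival, Section 7.2.1) does not depend on this point.

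**1. Required measurements.** Follow-up visits fall at 10-12 weeks and then 3-monthly to 24 months (Sections 6.2.3 and 6.3): 1 + 7 = about 8.

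| Test | Baseline | 10-12 weeks | Later visits (about 7) |
|---|---|---|---|
| Chemistry | required | optional | optional |
| Blood count | required | required | optional |

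Required chemistry after SBRT is 0 of about 8 visits; required blood counts are 1 of about 8. Twelve weeks is 84 days, just under 3 months. The 10-12 week visit is therefore the only follow-up visit in the acute window. All later visits fall in the late window, the only one in which kidney abnormality is named.

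**2. Expected reported rate.** Let p be the true proportion of patients who develop the abnormality. Let s be the probability that an affected patient is tested while abnormal and has the result recorded, at any time in the window. With all evaluable patients as denominator:

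expected reported rate = p × s, which is below p whenever s < 1.

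The relevant quantity is s, not the overall proportion tested. The two coincide only if testing is independent of toxicity, and testing on indication is not. The documents give neither p nor s. For assumed p = 10% and 50 evaluable patients:

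| Assumed s | Reported rate | Expected cases in 50 | Chance of no case, (1 − ps)^50 |
|---|---|---|---|
| 1.0 | 10% | 5.0 | 0.90^50 = 0.5% |
| 0.7 | 7% | 3.5 | 0.93^50 = 2.7% |
| 0.5 | 5% | 2.5 | 0.95^50 = 7.7% |
| 0.4 | 4% | 2.0 | 0.96^50 = 13.0% |

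**3. Reading a zero.** With 0 of 50, the exact 95% upper limit is 1 − 0.025^(1/50) = 7.1%. That limit bounds p × s, not p. At s = 0.5 it is compatible with p of about 7.1/0.5 = 14%. The planned interval does not show this.

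**4. Why tested patients alone are not a sufficient denominator.** If unaffected patients are tested with probability u, the rate among those tested is ps / [ps + (1 − p)u]. With assumed p = 10%, s = 0.7 and u = 0.4, this is 0.07 / (0.07 + 0.36) = 16%, above the true 10%. Under selective testing the all-evaluable rate is too low and the tested-only rate tends to be too high. Both are needed, and they converge as testing becomes routine.

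**5. Stopping rule.** Section 7.4 counts grade 3-5 toxicity only, and needs at least 4 events and an observed rate of at least 33%. The institutional experience in Section 1.3.1 is no grade 3-4 toxicity in 24 post-operative patients and 3 of 71 (4%) with acute grade 3 in intact disease. Nothing in the documents gives a rate of silent grade 3-5 liver or kidney events.

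**The case against.** The strongest reply is that this is a consistent and explicit choice. Text and table agree, and testing is left to clinicians who see the patient with history and examination at each follow-up visit. Toxicity is secondary, there is no second arm whose comparison could be distorted, and the primary endpoint is untouched. All of that stands. It limits the weight of the point without supplying the missing measurements.

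Four stronger readings are tempting and are not supported:

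- A reader might infer that these toxicities go undetected unless symptomatic. Clinical indication is wider than symptoms: patients are linked to a medical oncologist (Section 3.5), and tests ordered for systemic therapy would find some silent cases. Detection is selective, not absent.
- A reader might multiply a true rate by the proportion of patients tested. Suspicion prompts testing, and a persistent abnormality can be caught at any of several visits, so detection among affected patients may well exceed the overall proportion tested.
- A reader might infer that missed events never reach the stopping rule. Only silent grade 3-5 events are at issue. If 20% laboratory-only and 20% other grade 3-5 toxicity are assumed, the chance of stopping falls from 0.90 with full detection to 0.28 with none. Nothing in the documents supports 20%. The Section 1.3.1 series may themselves have under-ascertained, but they do not point that way.
- A reader might infer that the overall toxicity rate is biased low. Section 6.4.5 divides acute from late by timing alone, and Section 7.3.3 summarises attribution only for serious or grade 3 and higher events. Abnormal values due to chemotherapy or recurrence could enter the count, so the net direction for SBRT-caused toxicity is not established.

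**Conclusion.** The point holds as one of incomplete and selective ascertainment. No chemistry is required at any visit after SBRT, although liver and kidney abnormality are named risks and a baseline comparator exists. The all-evaluable rates of these abnormalities, from any cause, are therefore lower bounds.

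That direction needs only incomplete detection and the stated denominator. The size cannot be computed from the documents: 4-10% reported for a true 10% is an illustration resting on an assumed rate and on assumed detection of 40-100%. The consequence is confined to a secondary safety estimate. The point deserves correction because the remedy is cheap, not because the trial's main conclusion is at risk.

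**What to change.** **Section 6.2.4 and the Section 6.3 table.** Require creatinine, total bilirubin, AST, ALT and alkaline phosphatase at the 10-12 week visit, on the same draw as the mandatory blood count, and at the existing 3-monthly visits while the patient remains on follow-up. Accept any result already drawn for other care within a stated window.

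**Section 7.3.3.** Report the number of patients tested at each visit. Give laboratory toxicity rates with tested patients as denominator beside the all-evaluable rate. Apply the existing Section 8.2.1 attribution categories to these abnormalities at every grade, so that chemotherapy- or recurrence-related changes are distinguished from SBRT toxicity.

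**If no draws are added at the later visits,** state that late laboratory toxicity rates are lower bounds.

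**Cost.** A routine panel at up to about 8 scheduled visits per patient, falling only on those not already being tested and on fewer visits for those who leave follow-up early. Results drawn for other care need only transcription. The reporting changes need recording of who was tested, plus analysis work. Treatment is unaffected.
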